### Surveys

Participants will be asked to complete four surveys, including a baseline survey at the time of enrollment and three follow-up surveys, which will be designed to complement in-clinic assessments completed as a part of standard outpatient mental health care. To the extent possible, redundancy with in-clinic assessments (i.e., due to the Measurement-Based Care program) will be avoided. The first follow-up survey will occur at the end of 6 weeks post-enrollment, the second at the end of 18 weeks post-enrollment and the third at the end of 12 months post-enrollment.

Depending on waitlist length for outpatient mental health services, there may be variation in whether participants have engaged with clinical care by the time they complete their follow-up survey(s). Surveys will be administered by the predetermined schedule regardless of whether participants have engaged with care. The rationale for this decision, rather than scheduling follow-up surveys to coincide with the initiation of outpatient care:

1. There is a possibility that participants may never engage with outpatient care, and these non-engagers would never receive follow-up surveys
2. Waitlist time often varies between recruitment sites (i.e., UHS tends to have a shorter waitlist for care), which would create measurement biases (e.g., UHS patients may consistently engage in care with less time to engage with the app-based intervention)
3. Participants may be receiving other mental health care (e.g., via primary care), making it less important to time follow-up surveys with the initiation of outpatient mental health services
4. The existing timeline ensures all participants randomized to the groups receiving app-based interventions have received a reasonable 'dose' of the intervention prior to assessment
5. The existing timeline ensures that measurement will take place at generally the same time frame for all participants

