### OBJECTIVES

As part of the Precision Health initiative at the University of Michigan, this project is focused on the effects of wearable and mobile technology to both reduce mental health symptoms and predict response to clinic-based treatments.

The overall goal of this project is to reduce the burden of mental health conditions by two means:

- 1) Increasing capacity in the mental health care system through expanding use of mobile technology-delivered interventions.
- 2) Accelerating recovery by matching patients to the pharmacological, psychological, and mobile-based treatments from which they will likely derive the greatest benefit.

To do so, we will complete the following **specific aims**:

**Aim 1:** To assess the independent and combined effectiveness of two classes of mobile technology interventions among patients while on the waitlist for traditional care:

- (a) App-based cognitive behavioral and mindfulness interventions
- (b) Enhanced objective, mobile data feedback on mood, sleep, heart rate, and activity levels

**Aim 2:** To use machine learning to identify key predictors of treatment response from mobile technology,

genomic, and environmental data collected from patients receiving:

- (a) Mobile technology interventions while on a waitlist for outpatient mental health care
- (b) Traditional face-to-face psychotherapy, medication, or neuromodulation treatment

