## **RESEARCH DESIGN AND METHODS**

This study will have **two phases**, each with different study designs:

**Phase 1** will cover the period while individuals are waiting for care. The design of this phase is a randomized clinical trial, wherein participants are randomly assigned to one of three study conditions that vary by the type of Mobile Health (mHealth) intervention they can receive.

**Phase 2** begins when a participant has a first appointment for outpatient mental health care, and uses a cohort study design for measuring outcomes associated with clinic-based treatments.

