### **Phase 1**

Patients with scheduled intake mental health appointments, pre-screening mental health appointments, on the waitlist/referral list, or identified as a potential patient seeking mental health care at Michigan Medicine or University Health Services will be recruited to participate in the study. Patients can be recruited at any time between the appointment being scheduled to up to one month following their intake appointment.

Participants that are enrolled with sufficient time before their scheduled appointment ( $\geq 2$  weeks) will be randomized to one of **three groups**:

- 1) Enhanced Feedback + Standard Feedback (**EF+SF**): Participants will receive enhanced feedback from the MyDataHelps study app in addition to standard feedback from the Apple Watch health app or Fitbit activity tracker
- 2) App-Based Intervention + Standard Feedback (**App+SF**): Participants will receive an app-based intervention in addition to standard feedback from the Apple Watch health app or Fitbit activity tracker
- 3) App-Based Intervention + Enhanced Feedback + Standard Feedback (**App+EF+SF**): Participants will receive an app-based intervention, enhanced feedback from the MyDataHelps study app, and standard feedback from the Apple Watch health app or Fitbit activity tracker

Some patients may have a shorter waiting period (<2 weeks) prior to their intake appointment (e.g., due to acute mental health symptoms). These patients will also be contacted for recruitment to provide opportunity for benefit from the research and from access to the mHealth interventions and will still be randomized to one of the above-listed groups.

As part of the enrollment process, participants will be guided by a study team member through **three processes**:

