## **Phase 2**

Phase 2 begins when participants establish care with a clinical provider at Michigan Medicine Outpatient Psychiatry or UHS. In Phase 2, participants will engage with outpatient mental health care services as part of routine care, and the study will continue to gather both active and passive data on participants' symptoms and activity, similar to Phase 1. Participants will continue to have access to their assigned app-based intervention while concurrently receiving outpatient mental health services. The study will collect data from participants' phones and apps for up to one year following the initiation of clinical care or until participants have completed their 12-month follow-up survey. Participants may still remain enrolled in the study if they cease engagement with outpatient mental health care services during this phase.

*Summary of tasks that participants will be asked to complete during Phase 2:*

- Complete daily mental health symptom assessments via the MyDataHelps app
- Wear assigned device (Apple Watch or Fitbit) regularly for objective data collection
- Engage with assigned app-based intervention (Headspace or SilverCloud)
- Complete 6-week follow-up survey
- Complete 18-week follow-up survey
- Complete 12-month follow-up survey
- Provide a biological specimen (if not yet completed during Phase 1)

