## **Screening and Recruitment**

Participant screening and recruitment will be managed by study staff. All study team members are required to complete team/study training and all appropriate regulatory training and disclosures.

The study will recruit 4,500 participants via patients at Michigan Medicine and student patients at University Health Service (UHS). Potential study participants will include adult patients (age 18+) that are scheduled for an intake mental health appointment, pre-screening mental health appointment, on the waitlist/referral list, or identified as a potential patient seeking mental health at either Michigan Medicine or UHS. These appointments are generally scheduled with a 3-10 week waiting period. Patients will be invited to participate in the study as soon as possible after scheduling their appointment in order to best maximize participation during their full waiting period.

A waiver of HIPAA authorization is requested in order for study staff to:

- 1) Receive daily lists of patients for whom a mental health intake appointment has been scheduled at each recruitment site
- 2) Access the Michigan Medicine and UHS electronic health records to confirm eligibility of listed patients and obtain contact information

Study staff will employ the following **recruitment strategies** to contact, screen, and enroll potential participants:

1. At the time of scheduling their intake mental health appointment, patients may be informed by call center staff that they may be contacted about a new study.

2. Daily lists of newly scheduled appointments and individuals on the waitlist/referral list will be generated by the Michigan Medicine Department of Psychiatry call center, UHS scheduling, or from the Research Data Warehouse (RDW) and provided to study staff.
3. Using existing Research Data Warehouse information, a patient is prospectively identified as someone who meets the study criteria during the screening process. Potentially eligible patients may be contacted by email/text message/phone call to introduce the study, with an invitation to contact the study team by phone or email if interested in participating.
4. Prior to contacting patients by phone/text message/phone call, study staff will complete preliminary screenings via listed patients' electronic health records to determine whether basic, objective inclusion criteria are met (e.g., scheduled outpatient mental health appointment, age 18+).

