### **ANALYSIS PLAN**

A primary goal is to obtain information about the feasibility and acceptability of the use of app-based interventions and enhanced feedback in response to mobile health device use, as well as to estimate the distribution and variability of potential primary and secondary outcomes of interest. Data will be examined using standard univariate summary measures, bivariate statistical tests of association, and graphical displays. We will assess subjective and objective data in areas including mental health and physical health measures, substance use, and app use. This will assess responsiveness to the interventions as well as how best to provide clinicians with useful patient data that may help inform treatment decisions. This is a primary outcome for future work. Additional outcomes to be assessed are listed in Table 1.

We will calculate means and standard deviations for participant characteristics and outcomes measures at each assessment and also for change scores. With outcomes that are categorical, we will use the Chi square test, and with outcomes that are continuous, we will use t-tests to make comparisons.

We will also conduct baseline and ongoing analyses of the presence of genotype x stress interaction among this sample. For example, as a baseline analysis, we will investigate association between each variant/haplotype and PHQ (baseline) scores using linear regression. To explore gene x environment interactions, we will assess for association between each variant/haplotype and PHQ (change) scores.

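### Aim 1 concerns the waiting period, but the first post-baseline PHQ-9 and GAD-7 come at a fixed 6 weeks, and the planned t-tests do not separate the waitlist effect from the effect with care under way

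*Combined protocol and SAP*

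**What the plan says.** The Objectives section states Aim 1 as "To assess the independent and combined effectiveness of two classes of mobile technology interventions among patients while on the waitlist for traditional care". Research Design and Methods says that Phase 1, the randomized phase, "will cover the period while individuals are waiting for care". The Phase 2 section puts the boundary at the start of clinic care: "Phase 2 begins when participants establish care with a clinical provider at Michigan Medicine Outpatient Psychiatry or UHS".

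On timing, Screening and Recruitment says "These appointments are generally scheduled with a 3-10 week waiting period", and the Surveys section says "The first follow-up survey will occur at the end of 6 weeks post-enrollment". Table 1 places the PHQ-9, GAD-7, PANSI and PCL-5 at baseline, 6 weeks, 18 weeks and 12 months. The Surveys section acknowledges that participants will differ in whether they have reached care by a given survey, and it gives five reasons for keeping fixed dates. Recruitment is also wide: "Patients can be recruited at any time between the appointment being scheduled to up to one month following their intake appointment".

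For comparisons, the Analysis Plan offers chi-square tests for categorical outcomes and, for the rest, "with outcomes that are continuous, we will use t-tests to make comparisons". It mentions neither waiting time nor start of care.

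**The concern.** The aim, the phase definition and the analysis do not line up. Clinic treatment is a strong influence on PHQ-9 and GAD-7 scores. For anyone seen before week 6, every post-baseline value on these scales is taken with care under way, which is Phase 2 by the plan's own definition. A plain t-test at 6 weeks then mixes people still waiting with people in treatment.

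What is at stake is interpretation. If clinic care narrows the differences between arms, a small or null 6-week contrast could mean that the interventions do little while people wait, or that care has covered over a benefit that was there. The plan has no analysis that tells these apart, although Aim 1 turns on the distinction. The Surveys section notes that waits tend to be shorter at University Health Services, so the mixture is also likely to differ by site.

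**Working it through.** The plan states no share in care at week 6 and no power calculation, so there is no figure of its own to reproduce.

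**1. Which planned analysis gives the Aim 1 quantity?** The aim and Phase 1 are limited to waiting. The symptom scales first recur at week 6 irrespective of care. The 6-week survey is listed as a task under both phases. The Analysis Plan names no Aim 1 outcome or time point and has no rule for start of care. So no planned analysis isolates the waiting period.

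**2. How many could have an appointment by week 6?**

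Inputs from the documents:
- The wait W from scheduling is generally 3 to 10 weeks, with no mean or shape given (Screening and Recruitment).
- The survey falls 6 weeks after enrollment, not after scheduling (Surveys).
- The main randomized group has at least 2 weeks to go (Phase 1).
- Enrollment is complete only after the device, usually mailed, has arrived and been paired (Enrollment). The lag d from scheduling to enrollment is therefore probably above zero, but it is not stated.

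Assumptions: the shape of W, and d = 0, 1 or 2 weeks.

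*Uniform wait, at least 2 weeks left at enrollment.* With F(x) = (x − 3)/7, held between 0 and 1, the share is [F(6+d) − F(2+d)] / [1 − F(2+d)].
- d = 0: (3/7)/1 = 43%
- d = 1: (4/7)/1 = 57%
- d = 2: (5/7 − 1/7)/(6/7) = 4/6 = 67%

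The share reaches one half at d = 0.5, since (6.5 − 3)/7 = 0.5.

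*Wider assumptions.* Here the denominator is everyone whose appointment is still ahead at enrollment, so the share is F(6+d). Results are for d = 0 / 1 / 2.
- Triangular, peak at 10 weeks, F = ((x − 3)/7)²: 18% / 33% / 51%
- Triangular, peak at 6.5 weeks: 37% / 63% / 84%
- Triangular, peak at 3 weeks, F = 1 − ((10 − x)/7)²: 67% / 82% / 92%
- Uniform: 43% / 57% / 71%
- Uniform with 20% never engaging (× 0.8): 34% / 46% / 57%
- Uniform with 20% enrolled after intake or otherwise certain to be in care (0.2 + 0.8F): 54% / 66% / 77%

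These cases run from about 18% to 92%. Stacking assumptions widens the range a little: a late-peaked wait at zero lag with 20% never engaging gives 0.184 × 0.8 = 15%.

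**3. What can be conditioned on?** A scheduled date recorded before allocation cannot be affected by arm, so arm comparisons at a given scheduled wait remain randomized. The actual start of care comes after allocation and may be affected by arm. The scheduled date is largely in hand: the 2-week rule needs it, staff receive daily lists of new appointments, and they monitor upcoming appointments to avoid duplicate survey items (Self-Report Surveys).

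**The case against.** The strongest reply is that the choice was deliberate. The Surveys section discloses the variation and gives sensible reasons for fixed dates: people who never engage would otherwise have no follow-up, sites differ in wait, and everyone should have had a fair exposure to the app. The all-randomized contrast is also a legitimate effectiveness question, and randomization should balance care timing across arms. All of this stands. It supports the schedule and the pooled comparison, but it does not say what the 6-week contrast estimates.

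Four stronger readings are tempting and not supported:
- *Most participants are in care by week 6.* The documents give no such share. Week 6 against 3 to 10 weeks gives 43% under a uniform wait with no lag. The calculation also counts appointments, not attended care, and missed visits lower the figure.
- *There are no symptom data before week 6.* Mood is rated daily from enrollment, and a weekly suicide-risk item may be asked. Only the multi-item scales wait until week 6. The Analysis Plan does not, however, name daily mood as the Aim 1 outcome.
- *The randomized comparison is biased.* It is not. It answers a different question.
- *The loss of effect or power can be quantified.* The plan gives no effect by care status, standard deviation, allocation ratio or attrition, and not all of the 4,500 will have booked dates with at least 2 weeks to go.

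It is also fair to object that patients booked beyond week 6 are a selected group. They wait longest, they leave out referral-list patients without a date, and they may be receiving care elsewhere, as the Surveys section notes. Their estimate should not become the sole Aim 1 result.

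**Conclusion.** The concern holds as a gap in the analysis, not as a fault in the survey schedule. Aim 1 is about the waiting period, and no planned analysis separates it from the period after care begins. The share with an appointment by week 6 is unknown: 43-67% of those with at least 2 weeks to go under uniform waits and a 0 to 2 week lag, and about 18-92% across the wider cases. Even at the low end the 6-week contrast is a mixture, so the plan should say what it estimates. A null all-randomized result at 6 weeks would not show absence of benefit while waiting. The change is worth making because it is cheap and bears directly on the first aim. The size of any dilution cannot be given from these documents.

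**What to change.** Keep the survey schedule and the all-randomized 6-week comparison, labelled as the effect regardless of start of care. Then add to the Analysis Plan:

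1. Record the scheduled appointment date, or that none is booked, before allocation. Count weeks to appointment from a date no later than allocation, because installing the assigned app is itself an enrollment step and completed enrollment can therefore follow allocation.
2. Pre-specify a 6-week model for PHQ-9 and GAD-7 with arm, scheduled weeks to appointment and their interaction. Report the estimate for participants scheduled after week 6 as a supporting waitlist-period estimate that applies to longer-wait patients with booked dates.
3. Compare arms on the daily mood rating from enrollment up to the scheduled appointment. Report response rates by arm, since enhanced feedback may show participants their own ratings and so change how often they respond.
4. Report the share in care at week 6 by arm.
5. State that no analysis will subset on actual start of care, which is post-randomization.

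Also reconcile two passages. The Phase 1 section says patients with under 2 weeks to intake are still randomized to the three groups, while App-Based Interventions says they are outside the initial randomization. This changes who is in the comparison and the week-6 share.

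The cost is plan wording, one baseline date that is largely already held, and a little more analysis. The waitlist-period estimates will have wider intervals than the pooled one, and patients without a booked date will enter only the all-randomized estimate.

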### *Summary of tasks that participants will be asked to complete during Phase 1:*

- Complete daily mental health symptom assessments via the MyDataHelps app
- Wear assigned device (Apple Watch or Fitbit) regularly for objective data collection
- Engage with assigned app-based intervention (Headspace or SilverCloud) regularly
- Complete baseline assessment via the MyDataHelps app
- Complete 6-week follow-up survey

- Complete 18-week follow-up survey
- Complete 12-month follow-up survey
- Provide a biological specimen

## **Phase 2**

Phase 2 begins when participants establish care with a clinical provider at Michigan Medicine Outpatient Psychiatry or UHS. In Phase 2, participants will engage with outpatient mental health care services as part of routine care, and the study will continue to gather both active and passive data on participants' symptoms and activity, similar to Phase 1. Participants will continue to have access to their assigned app-based intervention while concurrently receiving outpatient mental health services. The study will collect data from participants' phones and apps for up to one year following the initiation of clinical care or until participants have completed their 12-month follow-up survey. Participants may still remain enrolled in the study if they cease engagement with outpatient mental health care services during this phase.

*Summary of tasks that participants will be asked to complete during Phase 2:*

- Complete daily mental health symptom assessments via the MyDataHelps app
- Wear assigned device (Apple Watch or Fitbit) regularly for objective data collection
- Engage with assigned app-based intervention (Headspace or SilverCloud)
- Complete 6-week follow-up survey
- Complete 18-week follow-up survey
- Complete 12-month follow-up survey
- Provide a biological specimen (if not yet completed during Phase 1)

## **Screening and Recruitment**

Participant screening and recruitment will be managed by study staff. All study team members are required to complete team/study training and all appropriate regulatory training and disclosures.

The study will recruit 4,500 participants via patients at Michigan Medicine and student patients at University Health Service (UHS). Potential study participants will include adult patients (age 18+) that are scheduled for an intake mental health appointment, pre-screening mental health appointment, on the waitlist/referral list, or identified as a potential patient seeking mental health at either Michigan Medicine or UHS. These appointments are generally scheduled with a 3-10 week waiting period. Patients will be invited to participate in the study as soon as possible after scheduling their appointment in order to best maximize participation during their full waiting period.

A waiver of HIPAA authorization is requested in order for study staff to:

- 1) Receive daily lists of patients for whom a mental health intake appointment has been scheduled at each recruitment site
- 2) Access the Michigan Medicine and UHS electronic health records to confirm eligibility of listed patients and obtain contact information

Study staff will employ the following **recruitment strategies** to contact, screen, and enroll potential participants:

1. At the time of scheduling their intake mental health appointment, patients may be informed by call center staff that they may be contacted about a new study.

2. Daily lists of newly scheduled appointments and individuals on the waitlist/referral list will be generated by the Michigan Medicine Department of Psychiatry call center, UHS scheduling, or from the Research Data Warehouse (RDW) and provided to study staff.
3. Using existing Research Data Warehouse information, a patient is prospectively identified as someone who meets the study criteria during the screening process. Potentially eligible patients may be contacted by email/text message/phone call to introduce the study, with an invitation to contact the study team by phone or email if interested in participating.
4. Prior to contacting patients by phone/text message/phone call, study staff will complete preliminary screenings via listed patients' electronic health records to determine whether basic, objective inclusion criteria are met (e.g., scheduled outpatient mental health appointment, age 18+).
5. Study staff will follow up with a phone call/text message/phone call within 2 business days of the patient's appointment scheduling to further describe the study and assess interest.
6. Patients identified by preliminary screenings as potentially eligible may be sent a standardized study letter by mail to introduce the study, with an invitation to contact the study team by phone/text message/email if interested in participating.
7. Interested patients will be asked additional screening questions to determine eligibility (e.g., owning a smartphone, willingness to keep study setup configured on smartphone for duration of study). Eligibility screening questions may be administered via phone contact with the potential participant or within the MyDataHelps app prior to consent.
8. Interested and eligible patients will be invited to the study via the RKStudio study portal email system and directed to download the MyDataHelps study app on their smartphone. Account creation within the app will facilitate participant access to the informed consent document and enrollment in the study.

Patients that have a short waiting period (<2 weeks) prior to their intake appointment will be offered the option to meet a study team member in person at the time of their clinic intake appointment for screening, consent, and enrollment. Study staff will conduct a preliminary screening via the electronic health record for eligibility, and will then contact potentially eligible participants by phone or email to offer a meeting at their first appointment to complete the study enrollment processes. If the patient does not show for the intake appointment, study staff will follow up by phone to offer further information and screening for the study. These participants may also opt to complete the study processes remotely (e.g., phone, app) or in a separate agreed-upon location (e.g., in the community), if desired.

